4.3.1.3 Descriptive Endpoints

Descriptive endpoints are reported using only summary statistics and no hypothesis tests will be performed. All mortality- and hospitalization-related components of the primary endpoints will be adjudicated by the CEC. The following additional data will be collected and reported:

- Cardiovascular mortality at 12 months post-implantation
- All-cause hospitalizations at 12 months post-implantation
- Frequency of subject PA pressure uploads through 12 months
- HF medication changes through 12 months
- PA pressure measurements from baseline through 12 months
- NT-proBNP (or BNP) at baseline, 6, and 12 months
- HFHs at 12 months post-implantation compared to HFHs in the 12 months prior to implantation

4.3.2 GUIDE-HF Single Arm

The GUIDE-HF Single Arm will evaluate one primary endpoint, several secondary endpoints, and several descriptive endpoints.

4.3.2.1 Primary Endpoint

The primary endpoint is a composite of recurrent HFHs or emergency department/hospital outpatient observation visits for intravenous diuretic therapy or all-cause mortality at 12 months post-implantation (same as for the Randomized Arm), to be compared between subjects with an elevated NT-proBNP (or BNP) only and subjects with a prior HFH only. Subjects who have both elevated NT-proBNP (or BNP) and a prior HFH will not be included in the analysis for the primary endpoint. All events contributing to the primary endpoint will be adjudicated by the CEC (see section 5.10.4 for details). In rare instances, CEC discretion may be used to determine whether additional criteria would identify a decompensation event that could represent a valid contribution to the primary endpoint (e.g., ultra-filtration in lieu of diuretics).

4.3.2.2 Secondary Endpoints

The secondary effectiveness endpoints are:

- Composite of recurrent HFHs or emergency department/hospital outpatient observation visits for intravenous diuretic therapy at 12 months post-implantation
- HFHs at 12 months post-implantation compared to HFHs in the 12 months prior to implantation. All subjects who receive a CardioMEMS™ PA Sensor implant will be included in the analysis of this endpoint.
- In addition, the individual components of the primary endpoint will each be evaluated as descriptive secondary effectiveness endpoints:
 - HFHs at 12 months post-implantation

- Emergency department/hospital outpatient observation visits for intravenous diuretic therapy at 12 months post-implantation
- All-cause mortality at 12 months post-implantation

The secondary safety endpoint is freedom from DSRCs at 12 months post-implantation. The secondary safety endpoint will be evaluated for all subjects enrolled in the Single Arm (i.e. with an attempted implant, whether successful or unsuccessful) and reported for the entire subject cohort and by subject group.

4.3.2.3 Descriptive Endpoints

Descriptive endpoints are reported using only summary statistics and no hypothesis tests will be performed. All mortality- and hospitalization-related components of the primary endpoints will be adjudicated by the CEC. The following additional data will be collected and analyzed. The EQ-5D-5L, KCCQ-12, and 6MHW test will be collected and reported only for the first 1000 subjects enrolled and successfully implanted in the Single Arm.

- Health status at baseline, 6, and 12 months post-implantation as assessed by EQ-5D-5L
- Health status at baseline, 6, and 12 months post-implantation as assessed by the KCCQ-12
- 6MHW test at baseline, 6, and 12 months post-implantation
- Cardiovascular mortality at 12 months post-implantation
- All-cause hospitalizations at 12 months post-implantation
- Frequency of subject PA pressure uploads through 12 months
- HF medication changes through 12 months
- PA pressure measurements from baseline through 12 months
- NT-proBNP (or BNP) at baseline, 6 months, and 12 months

4.4 Clinical Trial Population

The intended population for this clinical trial includes patients over the age of 18 years with symptomatic NYHA class II, III, or IV HF and either a prior HFH within the past 12 months and/or elevated NT-proBNP (or BNP) within 30 days prior to consent, that meet the trial entry criteria defined below. Refer to *Appendix C* for NYHA class definitions.

4.4.1 Inclusion Criteria

To participate in this clinical trial and receive a CardioMEMS™ HF System implant, subjects must meet all of the following inclusion criteria:

1. Diagnosis and treatment for HF (regardless of LVEF) for > 90 days prior to the date of consent:
 - a. Subjects should be on stable, optimally titrated medical therapy for at least 30 days, as recommended according to current AHA/American College of Cardiology (ACC) guidelines as standard-of-care for HF therapy in the United States, with any intolerance documented.
2. **GUIDE-HF Randomized Arm Only:** NYHA Class II, III or IV HF symptoms documented within 30 days prior to consent.
3. **GUIDE-HF Single Arm Only:** NYHA Class III HF symptoms documented within 30 days prior to consent.
4. HFH within 12 months prior to consent and/or elevated NT-proBNP (or BNP) within 30 days prior to consent defined as:
 - a. Subjects with LVEF ≤ 40%: NT-proBNP ≥ 1000 pg/mL (or BNP ≥ 250 pg/mL).
 - b. Subjects with LVEF > 40%: NT-proBNP ≥ 700 pg/mL (or BNP ≥ 175 pg/mL).
 - c. Thresholds for NT-proBNP and BNP (for both LVEF ≤ 40% and LVEF > 40%) will be corrected for BMI using a 4% reduction per BMI unit over 25 kg/m²
5. ≥ 18 years of age
6. Chest circumference of < 65 inches, if BMI is > 35 kg/m²
7. Written informed consent obtained from subject

8. Willing and able to upload PA pressure information and comply with the follow-up requirements

4.4.2 Exclusion Criteria

Subjects who meet any of the following criteria must be excluded from the clinical trial:

1. Intolerance to all neuro-hormonal antagonists (i.e., intolerance to angiotensin converting enzyme-inhibitors (ACE-I), angiotensin receptor blockers (ARB), angiotensin-neprilysin inhibitors (ARNi), hydralazine/isosorbide dinitrate **and** beta-blockers)
2. ACC/AHA Stage D refractory HF (including having received or currently receiving pharmacologic circulatory support with inotropes)
3. Received or are likely to receive an advanced therapy (e.g., mechanical circulatory support or cardiac transplant) in the next 12 months
4. NYHA Class IV HF patients with:
 - a. Continuous or chronic use of scheduled intermittent inotropic therapy for HF and an INTERMACS level of ≤ 4 , OR
 - b. Persistence of fluid overload with maximum (or dose equivalent) diuretic intervention
5. Glomerular Filtration Rate (eGFR) $< 25 \text{ mL/min}/1.73\text{m}^2$ and non-responsive to diuretic therapy, or receiving chronic dialysis
6. Inability to tolerate or receive dual antiplatelet therapy or anticoagulation therapy for one month post-implantation
7. Significant congenital heart disease that has not been repaired and would prevent implantation of the CardioMEMS™ PA Sensor
8. Implanted with mechanical right heart valve(s)
9. Unrepaired severe valvular disease
10. Pregnant or planning to become pregnant in the next 12 months
11. An active, ongoing infection, defined as being febrile, an elevated white blood cell count, on intravenous antibiotics, and/or positive cultures (blood, sputum or urine).
12. History of current or recurrent (≥ 2 episodes within 5 years prior to consent) pulmonary emboli and/or deep vein thromboses
13. Major cardiovascular event (e.g., unstable angina, myocardial infarction, percutaneous coronary intervention, open heart surgery, or stroke, etc.) within 90 days prior to consent
14. Implanted with Cardiac Resynchronization Therapy (CRT)-Pacemaker (CRT-P) or CRT-Defibrillator (CRT-D) for less than 90 days prior to consent
15. Enrollment into another trial with an active treatment arm
16. Anticipated life expectancy of < 12 months
17. Any condition that, in the opinion of the Investigator, would not allow for utilization of the CardioMEMS™ HF System to manage the subject using information gained from hemodynamic measurements to adjust medications, including the presence of unexpectedly severe pulmonary hypertension (e.g., trans-pulmonary gradient >15) at implant RHC, a history of non-compliance, or any condition that would preclude CardioMEMS™ PA Sensor implantation

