5.4.4 Implant Procedure

Once the subject has been determined to meet all eligibility criteria and provided informed consent, the subject will be scheduled for the implant/RHC procedure within 60 days of consent. Institutional standards should be followed for preoperative requirements. Implantation and baseline calibration of the CardioMEMS™ PA Sensor should be performed according to the CardioMEMS™ HF System user manual. The CardioMEMS™ HF System is considered investigational in this trial; however all other aspects of the IFU apply and should be followed. In the event that an alternative implantation approach is pursued, the alternative implantation approach and associated justification must be reported as a protocol deviation.

All enrolled subjects will be provided with trial ID cards instructing non-trial

providers to notify the trial research team upon presentation or admission to a hospital. Following randomization, data for subjects within the Randomized Arm are no longer to be viewed on the CardioMEMS™ Hospital Electronic Unit, so as to prevent Investigator access to PA pressure. Cards for Randomized Arm subjects will additionally specify to non-trial providers not to use the Hospital Electronic Unit. [REDACTED]

5.4.4.1 *Unsuccessful implant*

If an implant is attempted, but is unsuccessful, the subject should not be randomized, and associated information must be documented on the applicable CRF. If a reattempt is medically appropriate and planned, and there is no change in the subject's eligibility status, the implant can be rescheduled within 30 days. If clinically appropriate, the subject can be rescreened at a later date. Subjects with an attempted, but unsuccessful, implant, with no plan to be re-attempted, will be followed for 30 days post-implantation attempt, to document CardioMEMS™ PA Sensor/implant-related AEs. After 30 days, the subject will no longer participate in the trial and the applicable CRF must be completed. The 30 day follow-up may be conducted remotely.

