3.1.2 GUIDE-HF Single Arm

The GUIDE-HF Single Arm is a prospective, multi-center, single-arm clinical trial of the CardioMEMS™ HF System in North America in NYHA Class III HF patients, with either elevated NT-proBNP (or BNP) and/or a prior HFH. After signing the Informed Consent Form and confirmation of meeting all entry criteria for the Single Arm, subjects will complete baseline assessments. Within 30 days of consent, subjects will receive a CardioMEMS™ HF System. Subjects will be considered enrolled in the Single Arm once all entry criteria are met, informed consent is provided, and implantation of the CardioMEMS™ PA Sensor is attempted. However, subjects will only contribute towards the endpoint analysis following successful implantation. Subjects will upload PA pressure information daily, and receive HF management guided by PA pressure information.

The GUIDE-HF Single Arm will enroll approximately 2600 subjects at approximately 140 sites. Each subject will be followed for 12 months, with follow-up visits at 6 and 12 months.

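### Exclusions 13 and 14 look back only from consent, but implant may follow up to 60 days later, so a major cardiovascular event or new CRT device in between meets neither item

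*Protocol*

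**What the plan says.** **Event windows (Protocol 4.4.2).** Exclusion 13 covers major cardiovascular events, and its wording ends "percutaneous coronary intervention, open heart surgery, or stroke, etc.) within 90 days prior to consent". Exclusion 14 covers a recently implanted CRT-P or "CRT-Defibrillator (CRT-D) for less than 90 days prior to consent". Exclusion 12 reads "History of current or recurrent (≥ 2 episodes within 5 years prior to consent) pulmonary emboli and/or deep vein thromboses". Its recurrent clause is dated from consent; its reference to a current episode is not.

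**Time to implant.** Protocol 4.1.2 (Randomized Arm) and 4.1.3 (Single Arm) both allow 60 days from consent, and 5.4.4 says for both arms that "the subject will be scheduled for the implant/RHC procedure within 60 days of consent". Section 5.4.11 makes the successful implant date time zero, and the primary endpoints run for 12 months from implantation.

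**Eligibility checks.** Table 2 marks the assessment of entry criteria at Baseline only, with a footnote that cannot be read in the public text. Section 5.3 treats a consented subject who fails an entry criterion before an attempted implant as a screening failure. Section 5.4.4.1 allows a re-attempt after an unsuccessful implant on condition that "there is no change in the subject's eligibility status". No corresponding condition is visible for the first attempt.

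**The SAP on the same interval.** SAP 3.1.2 says of the Single Arm: "Within 30 days of consent, subjects will receive a CardioMEMS™ HF System". The interval for the Randomized Arm in SAP 3.1.1 is redacted.

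**The concern.** A 90-day look-back that ends at consent leaves the time from consent to implant uncovered. A subject who has a stroke on day 20 after consent and is implanted on day 50 has had it 30 days before the procedure, and neither item 13 nor item 14 is met. The same stroke 30 days before implant would exclude a subject who consented on the day of implant. An older event therefore excludes where a more recent one does not.

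The stakes are patient safety and the make-up of the population. A subject may undergo an invasive procedure soon after a major event, or enter follow-up with a CRT device only days old. Such an event may also go unrecorded as history. Cardiovascular and CRT history is taken at the baseline visit (5.4.3), and safety reporting begins with the implant attempt (8.2), although Table 2 marks reportable adverse events at Baseline if applicable.

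**Working it through.** The plan gives no figure to reproduce. The check is interval arithmetic on the stated windows, then a test of whether another provision closes the gap, then a rough scale.

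**Inputs**
- Look-back in exclusions 13 and 14: 90 days, ending at consent (4.4.2).
- Consent to implant: up to 60 days (4.1.2, 4.1.3, 5.4.4); up to 30 days for the Single Arm in SAP 3.1.2.
- Re-attempt after a failed implant: within a further 30 days (5.4.4.1).
- Planned subjects: 3600, of whom 1000 are in the Randomized Arm and 2600 in the Single Arm (Protocol 6.5).
- Annual rate of a listed event or new CRT device: not in the documents. I assume 5% to 10%, with 2% to 20% as a wider range.

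**Step 1: the windows.** Let g be the number of days from consent to implant. The earliest excluded event lies 90 + g days before implant. Events 0 to g days before implant fall after consent and are not covered.

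| Case | g (days) | Earliest excluded event, days before implant | Not covered, days before implant |
|---|---|---|---|
| Protocol limit | 60 | 90 + 60 = 150 | 0 to 60 |
| SAP limit, Single Arm | 30 | 90 + 30 = 120 | 0 to 30 |
| Re-attempt 30 days after a day-60 attempt | 90 | 90 + 90 = 180 | 0 to 90 |

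**Step 2: does another provision close the gap?**
- The screening-failure rule (5.3) acts on subjects who fail a criterion. A post-consent event is never prior to consent, so these subjects fail neither item 13 nor item 14.
- The re-attempt condition (5.4.4.1) does not apply to a first attempt. Even on a re-attempt it refers back to the same windows.
- Exclusion 17 is not tied to consent and reaches findings at the implant catheterization. It can remove some of these subjects, but it rests on the investigator's opinion and sets no fixed window.
- Under exclusion 12, a post-consent embolus or thrombosis may still exclude as a current episode. Only the count of recurrent episodes stops at consent.

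**Step 3: scale.** P(event in the gap) = 1 − exp(−rate × g/365), with g = 60:
- 5% per year: 1 − exp(−0.05 × 60/365) = 0.82%, and 3600 times the unrounded value is 29.5.
- 10% per year: 1 − exp(−0.10 × 60/365) = 1.63%, and 3600 times the unrounded value is 58.7.
- 2% to 20% per year: 0.33% to 3.23%, or about 12 to 116 of 3600.

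With the SAP's 30 days, which is documented for the Single Arm only, 5% to 10% gives 0.41% to 0.82%, or about 11 to 21 of 2600. At each assumed rate these counts are upper bounds, because every subject is taken to wait the full gap and none is removed under exclusion 17.

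**The case against.** The strongest reply is that the plan dates its windows from consent throughout (inclusions 1 to 4 as well as exclusions 12 to 14), and that nothing visible says the 90 days was meant to separate the event from the implant. On that view this is a convention. Other controls also remain active until the attempt: undated criteria such as Stage D disease and active infection, the screening-failure rule, exclusion 17, and the institutional preoperative standards and instructions for use cited in 5.4.4.

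Part of this stands. The purpose of the 90 days is inferred, and some affected subjects would be stopped in practice. But none of these controls applies the window itself to an event after consent, and a rule that excludes the older event and admits the newer one is hard to defend on any purpose.

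A reader might infer four stronger points, which the documents do not support:
- **That exclusions 3 and 16 share the defect.** They read "Received or are likely to receive an advanced therapy (e.g., mechanical circulatory support or cardiac transplant) in the next 12 months" and "Anticipated life expectancy of < 12 months". Neither is dated from consent, so no number of uncovered follow-up days can be derived from them.
- **That the Randomized Arm comparison is biased.** Randomization follows implant, so any event in the gap precedes allocation.
- **That the Single Arm comparison is biased.** Its groups are not randomized, but nothing shows that gap events would differ between them. SAP 5.2.1.2 names a propensity stratification method whose content is redacted, so the adjustment cannot be judged.
- **That the two documents conflict on timing in both arms.** The conflict is visible only for the Single Arm.

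**Conclusion.** The point holds for exclusions 13 and 14 and, narrowly, for the recurrent clause of exclusion 12. Up to 60 days before implant are outside these windows under the protocol, and only a discretionary criterion is left to act on an event in that time. The consequence is for patient safety and for who enters the population. No power, alpha or sample size figure changes.

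The numbers are small: at most about 29 to 59 of 3600 subjects, resting on the assumed 5% to 10% annual rate and a full 60-day wait. The gap itself depends on neither assumption. It does rest on the visible text, since parts of the protocol and the footnote to the eligibility row of Table 2 cannot be read.

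The Single Arm mismatch between 60 and 30 days is a separate inconsistency and stands on its own. Which limit is right is not judged here. The wording should be corrected, chiefly because doing so is cheap.

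**What to change.** 1. **Extend the windows without moving them.** Keep the pre-consent windows and state that exclusions 12 (recurrent clause), 13 and 14 also apply to events between consent and the implant attempt. Simply replacing consent with implant as the reference date would loosen the rule. An infarction 40 days before consent is excluded now; with implant on day 55 it would lie 40 + 55 = 95 days before implant and become admissible. With a 60-day gap, events 31 to 90 days before consent could drop out in this way (31 + 60 = 91).
2. **Add a check to 5.4.4.** Before the first implant attempt, require an interval history since baseline and confirmation that the subject is still eligible, as 5.4.4.1 already requires for a re-attempt. The baseline history cannot serve, because it may have been taken before the event. Subjects who no longer qualify become screening failures and may be rescreened under 5.4.3.1.
3. **Reconcile the Single Arm limit** between Protocol 4.1.3 and SAP 3.1.2.

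The cost is wording, one checklist line with a short interval history, and a few extra or delayed screening failures. No new test is needed.

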4.4.3 Enrollment of Medicare Beneficiaries

This clinical trial will enroll appropriate Medicare beneficiaries that qualify based on the inclusion and exclusion criteria set forth in the trial. This IDE clinical trial adheres to all standards of Medicare coverage requirements set forth by the IDE and clinical trial coverage policies of the Center for Medicare and Medicare Services (CMS). Section 7, Risks and Benefits, describes how all enrolled subjects, including Medicare beneficiaries, may be affected by the CardioMEMS™ HF System under investigation.

Subjects enrolled in the clinical trial are expected to be consistent with the Medicare population based on demographic characteristics and cardiovascular risk factors; therefore, the clinical trial results are expected to be generalizable to the Medicare population.

4.4.4 Historically Underrepresented Demographic Subgroups

The Sponsor intends to implement FDA's guidance on sex-specific data in medical device clinical studies to ensure adequate representation of women and other traditionally under-represented demographic subgroups in this clinical trial.

The Sponsor will take the following steps to ensure adequate representation of women and racial or ethnic minorities in this clinical trial:

- The Sponsor will provide training to investigational site personnel to ensure adequate representation of these demographic subgroups
- The Sponsor will regularly review enrollment data to investigate whether there is under-representation of these demographic subgroups
- The Sponsor will regularly review withdrawal rates for under-represented subgroups and compare these rates with that in the overall clinical trial population
- As appropriate and necessary, the Sponsor will retrain sites on the importance of recruiting and retaining subjects in the clinical trial
- The Sponsor will approach sites without bias or consideration for specific demographic subgroups
- The Sponsor will have the Informed Consent Forms in alternative languages and will work with sites and IRBs/ECs on recruitment materials

5 Clinical Trial Procedures

All parties involved in the conduct of this clinical trial will be qualified by education, training, or experience to perform their tasks, and this training will be documented appropriately. The investigation will not commence until the Sponsor receives written approval from the Institutional Review Board (IRB)/Ethics Committee (EC) and relevant regulatory authorities, and all required documents have been collected from the investigational site(s). All trial staff will be required to undergo training prior to performing any trial-related activities. Approval from the Sponsor must be received prior to initiating clinical trial procedures.

An overview of the study procedures is shown in Figure 1. Following consent, confirmation of eligibility, and baseline assessments, subjects will undergo a procedure to implant the CardioMEMS™ PA Sensor. After discharge from hospitalization post-procedure, subjects will have phone contact and follow-up visits at 6 and 12 months. If any CardioMEMS™ PA Sensor inaccuracy is suspected at any point, contact Sponsor's technical support for instructions to re-calibrate the CardioMEMS™ PA Sensor baseline. Upon completion of the 12 month follow-up visit, subjects will have completed the follow-up requirements of this clinical trial. The Principal Investigator should arrange for appropriate care of subjects following trial completion. After completing the 12 month visit, at the discretion of the clinician, Control Group subjects in the Randomized Arm may be treated with clinician knowledge of their PA pressure. The Sponsor must be notified if a site intends to view PA pressure data for a Control Group subject following the 12 month follow-up visit.

[REDACTED]

The following sections provide a detailed description of procedures required by this CIP.

[REDACTED]

[REDACTED]

